#### **9.2.2. Complaint Handling**

Lilly collects product complaints on investigational products and drug delivery systems used in clinical trials in order to ensure the safety of study participants, monitor quality, and to facilitate process and product improvements.

Subjects should be instructed to contact the investigator as soon as possible if he or she has a complaint or problem with the investigational product so that the situation can be assessed.

### **9.3. Treatment of Overdose**

For the purposes of this study, an overdose of tirzepatide is considered any dose higher than the assigned dose. The treatment for an overdose of tirzepatide is supportive care.

Refer to the IB for tirzepatide.

### **9.4. Safety**

#### **9.4.1. Clinical Laboratory Tests**

For each subject, laboratory tests detailed in [Appendix 2](#) should be conducted according to the Schedule of Activities (Section 2).

Additional blood draws may be drawn for safety purposes at the investigator's discretion.

##### **9.4.1.1. Amylase and Lipase Measurements**

Serum amylase and lipase measurements will be collected as part of the clinical laboratory testing and as specified in the Schedule of Activities (Section 2). Additional measurements may be performed at the investigator's discretion. Further diagnostic assessments will be recommended as per the algorithm (refer to [Appendix 7](#)) for the monitoring of pancreatic events whenever lipase and/or amylase is confirmed to be  $\geq 3 \times$  ULN at any visit postdose, even if the subject is asymptomatic.

### **9.4.2. Glucose Monitoring**

For safety purposes, blood glucose measurements will be performed using a bedside glucose monitor as specified in the Schedule of Activities (Section 2). Additional safety blood glucose measurements may also be taken during the study as deemed necessary by the investigator.

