Blood Glucose Monitoring (hours)			Predose, 8, 12	24, 36	48	72	96	X	X	X		Performed using a bedside glucose monitor. Additional measurements may be taken at the discretion of the investigator as clinically indicated.
PK Sampling (hours)			Predose, 8, 12	24	48	72	96	168	336	X		The exact time of sampling must be recorded.

Abbreviations: AE = adverse event; CRU = clinical research unit; D = day; ECG = electrocardiogram; ED = early discontinuation; PK = pharmacokinetic(s);

TE ADA = treatment-emergent antidrug antibodies.

Note: All sampling times are given relative to dosing (Time 0 hour) with tirzepatide (predose or hours postdose).

If multiple procedures take place at the same time point, the following order of the procedures should be used: ECGs, vital signs, clinical laboratory sample, PK sample (record of actual PK sampling time is the priority), immunogenicity, blood glucose and pharmacogenetic sample.

a Specified times are approximate and actual times will be recorded. Actual time should not exceed 1 hour prior to dosing for the predose assessment.

b Screening sample and any unscheduled samples for immediate safety assessments may be performed by the local laboratory affiliated with the sites. All other scheduled clinical safety laboratory samples will be assayed by a central laboratory for study reporting purpose.

c At least 28 days postdose or within 7 to 14 days upon confirmation of early discontinuation.

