### 3. Introduction

#### 3.1. Study Rationale

Tirzepatide (LY3298176) is a dual agonist of glucose-dependent insulinotropic polypeptide (GIP) and glucagon-like peptide-1 (GLP-1) receptors being developed for the treatment of type 2 diabetes mellitus (T2DM). As the patient population for tirzepatide may include patients with hepatic impairment, it is important to ascertain whether tirzepatide can be safely prescribed to this population without dose adjustment, once marketed. Tirzepatide is a synthetic peptide conjugated to a C20 fatty di-acid moiety and is presumed to be degraded into component amino acids by protein catabolism pathways. It is not expected to be biotransformed by drug metabolizing enzymes. However, the fatty acid component is expected to bind to albumin, thereby leading to a prolonged half-life, which supports a once weekly dosing regimen. Albumin concentration in hepatic impaired subjects can be lower than that seen in control subjects.

The liver plays a central role in glucose metabolism. Almost all patients with cirrhosis are insulin-resistant, 60% to 80% are glucose intolerant, and about 20% develop diabetes [Honda F et al 2018]. The main feature of blood glucose dynamics in patients with chronic liver disease (CLD) is marked blood glucose fluctuations, such as postprandial hyperglycemia and hypoglycemia. To address this issue, regular blood glucose monitoring has been included in the Schedule of Activities. Additionally, Study I8F-MC-GPGQ (GPGQ) will evaluate the pharmacokinetics (PK) of tirzepatide in subjects with hepatic impairment compared to healthy control subjects to investigate the impact of hepatic impairment, if any, on the PK profile of tirzepatide.

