#### **9.4.2.1. Hyperglycemia and Hypoglycemia Reporting**

Episodes of hyperglycemia (fasting plasma/serum glucose  $>270$  mg/dL [15 mmol/L]) or hypoglycemia (plasma/serum glucose  $\leq70$  mg/dL [3.9 mmol/L]) will be reported by the investigator or designated physician who will be responsible for advising the subject on what further actions to take. Additional monitoring may be requested at the investigator's discretion.

If the fasting plasma/serum glucose during the dosing period exceeds the acceptable level defined as hyperglycemia on 3 or more separate days over any 2-week period between screening and the end of the dosing period, the subject will be evaluated further at the study site. If fasting plasma/serum glucose continues to exceed the acceptable level, treatment with an appropriate antidiabetic agent may be initiated by the investigator. If hyperglycemia occurs during the follow-up period, the subject will remain in the study until completion of the planned follow-up.

Hypoglycemia episodes will be recorded on specific eCRF pages. Hypoglycemia will be treated appropriately by the investigator and additional monitoring of plasma/serum glucose levels may be performed. The following categories of the 2017 American Diabetes Association position statement on glycemic targets (ADA 2017) based on recommendations of the International Hypoglycaemia Study Group (IHSG 2017) should be applied for reporting in the eCRF and evaluating hypoglycemic events.

Hypoglycemia will be described using the following definitions:

- **Documented Glucose Alert Level (Level 1), Plasma Glucose (PG)  $\leq70$  mg/dL (3.9 mmol/L):**
  - **Symptomatic hypoglycemia:** an event during which typical symptoms of hypoglycemia are accompanied by PG  $\leq70$  mg/dL (3.9 mmol/L)
  - **Asymptomatic hypoglycemia:** an event not accompanied by typical symptoms of hypoglycemia but with PG  $\leq70$  mg/dL (3.9 mmol/L)
  - **Unspecified hypoglycemia:** an event during which PG  $\leq70$  mg/dL (3.9 mmol/L) but no information relative to symptoms of hypoglycemia was recorded
- **Documented Clinically Significant Hypoglycemia (Level 2) PG  $<54$  mg/dL (3.0 mmol/L):**
  - **Symptomatic hypoglycemia:** an event during which typical symptoms of hypoglycemia are accompanied by PG  $<54$  mg/dL (3.0 mmol/L)
  - **Asymptomatic hypoglycemia:** an event not accompanied by typical symptoms of hypoglycemia but with PG  $<54$  mg/dL (3.0 mmol/L)

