9.5.4 Glucose Monitoring and Hyperglycemia/Hypoglycemia Reporting

Hypoglycemic events will be appropriately recorded in the CRF. In the case of a hypoglycemic event, the actual blood glucose value, if measured, will be recorded in the CRF, together with any treatments administered. Each category of hypoglycemic event (defined in Section 9.4.2.1 of the Protocol) will be listed and summarized by group.

Blood glucose levels will be listed for individual patients and summarized by group.

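### By-group counts of asymptomatic and unspecified hypoglycemia do not separate scheduled from discretionary glucose readings, so unequal testing, if it occurs, would look like a group difference

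*Protocol*

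**What the plan says.** The row "Blood Glucose Monitoring (hours") in the protocol's Schedule of Activities (Section 2) sets bedside readings at predose, 8, 12, 24, 36, 48, 72 and 96 hours, Day 8, Day 15 and follow-up. That is 11 readings, 10 of them postdose, and it is the same for all four groups.

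More readings are allowed in three places:
- Schedule of Activities, comment on that row: "Additional measurements may be taken at the discretion of the investigator as clinically indicated".
- Section 9.4.2: "Additional safety blood glucose measurements may also be taken during the study as deemed necessary by the investigator".
- Section 9.4.2.1, after a hypoglycemic episode: "additional monitoring of plasma/serum glucose levels may be performed".

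None of these fixes a number or a time. Section 7.3 makes the study open-label.

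Section 9.4.2.1 defines asymptomatic hypoglycemia as "an event not accompanied by typical symptoms of hypoglycemia but with PG" at or below 70 mg/dL (Level 1) or below 54 mg/dL (Level 2). The unspecified category uses the same thresholds where no symptom information was recorded. Neither definition is restricted to scheduled readings. On recording, the section says "Hypoglycemia episodes will be recorded on specific eCRF pages".

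SAP 9.5.4 then says: "Each category of hypoglycemic event (defined in Section 9.4.2.1 of the Protocol) will be listed and summarized by group". It also lists glucose values by subject and summarises them by group. It does not say which readings may give rise to an event.

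**The concern.** A symptomatic or severe episode can come to notice without a planned reading. An asymptomatic low cannot, and an unspecified event also requires a glucose value. For these two categories the number of events found depends on how often the subject is tested as well as on how often glucose is low.

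The protocol gives the investigator a reason to watch impaired subjects more closely. Section 3.1 says that the main feature of glucose dynamics in chronic liver disease "is marked blood glucose fluctuations, such as postprandial hyperglycemia and hypoglycemia". Section 3.3 lets the investigator extend the inpatient stay for safety monitoring. Group 1 is restricted to healthy subjects, while type 2 diabetes is provided for alongside hepatic impairment.

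If that leads to more readings in Groups 2 to 4, the table would show an excess of hypoglycemia over controls that comes from ascertainment. The secondary objective compares safety and tolerability between these groups, and Section 9.4.7 names hypoglycemia as an event of interest. A reader of the planned table could not tell a testing effect from an effect of drug or disease.

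**Working it through.** Neither document gives a hypoglycemia rate, an expected number of extra readings or a power statement for this outcome, so there is no planned figure to reproduce. The check asks how large a false difference could be when the true chance per reading is the same in both groups.

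**From the documents:** 10 scheduled postdose bedside readings per subject; about 6 subjects in each impaired group, with 2 to 3 possibly accepted in Group 4.

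**Assumed, not in the documents:** 10 extra readings per subject in the more-tested group; a chance *p* of 1%, 3% or 5% that a reading is low without symptoms; extra readings taken without regard to symptoms or earlier lows.

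**Formula, independent readings:** P(at least one low in *k* readings) = 1 − (1 − *p*)^*k*. For *p* = 1%, 1 − 0.99^10 = 9.6% and 1 − 0.99^20 = 18.2%.

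**Formula, correlated readings:** a beta-binomial with mean *p* and within-subject correlation 0.3, which allows some subjects to be prone to lows. P(at least one low) = 1 − B(a, b + *k*)/B(a, b), where a = *p*(1 − 0.3)/0.3 and b = (1 − *p*)(1 − 0.3)/0.3.

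| *p* | Independent: 10 vs 20 readings | Gap | Correlation 0.3: 10 vs 20 readings | Gap |
|---|---|---|---|---|
| 1% | 9.6% vs 18.2% | 8.7 points | 4.2% vs 5.6% | 1.4 points |
| 3% | 26.3% vs 45.6% | 19.4 points | 12.3% vs 16.0% | 3.7 points |
| 5% | 40.1% vs 64.2% | 24.0 points | 19.7% vs 25.3% | 5.6 points |

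(Gaps are from unrounded values.) The range is therefore about 1 to 24 points. In a group of 6 that is 6 × 0.014 ≈ 0.1 to 6 × 0.240 ≈ 1.4 subjects.

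**Scheduled laboratory glucose.** Hypoglycemia is defined on plasma or serum glucose, and fasting glucose is in the chemistry panel (Appendix 2). The Schedule and Appendix 5 imply 4 to 5 postdose laboratory samples. Adding them to both groups, with *p* = 5% and independent readings:
- 14 vs 24 readings: 51.2% vs 70.8%, gap 19.6 points.
- 15 vs 25 readings: 53.7% vs 72.3%, gap 18.6 points.

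The largest gap falls from 24 to about 19 to 20 points.

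**Chance in small groups.** Take 6 subjects per group, *p* = 2% and independent readings (18.3% affected with 10 readings, 33.2% with 20). The comparison is of the number of affected subjects in groups A and B, by exact binomial calculation:

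| Testing | A more than B | A fewer than B | Tie |
|---|---|---|---|
| 10 readings in both | 34.9% | 34.9% | 30.3% |
| 20 in A, 10 in B | 60.8% | 17.1% | 22.1% |

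Unequal testing tilts the comparison but does not fix its result. Counts already differ about 70% of the time with equal testing.

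**The case against.** The strongest reply is that the documents do not show unequal testing. The discretion is the same for every group, and the protocol's stated answer to glucose instability in liver disease is a uniform schedule of readings. This stands: the bias is conditional.

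Second, the likely triggers for an extra reading are symptoms or a previous low. A low found because of symptoms is classed as symptomatic, and a repeat after a low adds no newly affected subject. This also stands, and it means that 10 extra readings unrelated to either trigger probably overstates the effect. It does not cover precautionary readings in a subject who looks at risk, which the wording also allows.

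Third, glucose values are to be listed by subject, so a careful reader could reconstruct the testing. That is only partly an answer, because the by-group table is what will be compared and it carries no count of readings.

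Fourth, the secondary endpoint is the incidence of adverse events. Hypoglycemia has its own eCRF module, no safety inference is planned, and chance dominates in groups of this size. All of this limits the importance of the point.

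Two stronger readings are tempting. One is that the SAP has decided to pool scheduled and unscheduled readings; it is silent, and pooling is only inferred from the absence of a restriction. The other is that the whole hypoglycemia summary, including Overall, should rest on scheduled readings alone. Protocol Section 9.4.2.1 defines Overall as combining every case, so that change would contradict it and would move genuine off-schedule lows, including those below 54 mg/dL, out of the main table.

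**Conclusion.** The point holds in a conditional form. SAP 9.5.4 cannot separate a testing effect from a group effect for asymptomatic and unspecified hypoglycemia. If Groups 2 to 4 are tested more often at the same true rate per reading, their incidence of these two categories is inflated in expectation. The direction follows from the arithmetic. The size does not: 1 to 24 percentage points rests on an assumed 10 extra readings and assumed rates of 1% to 5%, and it shrinks with within-subject correlation or when laboratory glucose is counted.

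Symptomatic, probable symptomatic and severe events are outside the point. This is a cheap improvement to a descriptive table; it does not threaten the trial's main conclusions.

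**What to change.** In SAP 9.5.4:

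1. Keep the summary of every category from all sources, with Overall still combining all cases as the protocol defines it.
2. For asymptomatic and unspecified events, at Levels 1 and 2, add a by-group row limited to scheduled postdose glucose values, and name it as the row for between-group comparison. State whether scheduled means bedside only or bedside plus central laboratory.
3. Add a row for events of these two categories found only at unscheduled readings.
4. Report the number of postdose glucose readings per subject by group.

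With the scheduled-only row, equal true rates give equal expected incidence: at *p* = 2% and 10 bedside readings, 18.3% in each group, with a chance excess equally likely either way (34.9% each).

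The cost is SAP wording and a few table rows. The scheduled-only row will hold fewer events, so it will be less precise. No event leaves the report, and discretionary testing and clinical care do not change. Item 4 assumes that unscheduled readings are entered in the database whether or not they are low; the documents do not say so, and this should be confirmed.

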#### **9.4.2.1. Hyperglycemia and Hypoglycemia Reporting**

Episodes of hyperglycemia (fasting plasma/serum glucose  $>270$  mg/dL [15 mmol/L]) or hypoglycemia (plasma/serum glucose  $\leq70$  mg/dL [3.9 mmol/L]) will be reported by the investigator or designated physician who will be responsible for advising the subject on what further actions to take. Additional monitoring may be requested at the investigator's discretion.

If the fasting plasma/serum glucose during the dosing period exceeds the acceptable level defined as hyperglycemia on 3 or more separate days over any 2-week period between screening and the end of the dosing period, the subject will be evaluated further at the study site. If fasting plasma/serum glucose continues to exceed the acceptable level, treatment with an appropriate antidiabetic agent may be initiated by the investigator. If hyperglycemia occurs during the follow-up period, the subject will remain in the study until completion of the planned follow-up.

Hypoglycemia episodes will be recorded on specific eCRF pages. Hypoglycemia will be treated appropriately by the investigator and additional monitoring of plasma/serum glucose levels may be performed. The following categories of the 2017 American Diabetes Association position statement on glycemic targets (ADA 2017) based on recommendations of the International Hypoglycaemia Study Group (IHSG 2017) should be applied for reporting in the eCRF and evaluating hypoglycemic events.

Hypoglycemia will be described using the following definitions:

- **Documented Glucose Alert Level (Level 1), Plasma Glucose (PG)  $\leq70$  mg/dL (3.9 mmol/L):**
  - **Symptomatic hypoglycemia:** an event during which typical symptoms of hypoglycemia are accompanied by PG  $\leq70$  mg/dL (3.9 mmol/L)
  - **Asymptomatic hypoglycemia:** an event not accompanied by typical symptoms of hypoglycemia but with PG  $\leq70$  mg/dL (3.9 mmol/L)
  - **Unspecified hypoglycemia:** an event during which PG  $\leq70$  mg/dL (3.9 mmol/L) but no information relative to symptoms of hypoglycemia was recorded
- **Documented Clinically Significant Hypoglycemia (Level 2) PG  $<54$  mg/dL (3.0 mmol/L):**
  - **Symptomatic hypoglycemia:** an event during which typical symptoms of hypoglycemia are accompanied by PG  $<54$  mg/dL (3.0 mmol/L)
  - **Asymptomatic hypoglycemia:** an event not accompanied by typical symptoms of hypoglycemia but with PG  $<54$  mg/dL (3.0 mmol/L)
  - **Unspecified hypoglycemia:** an event during which PG  $<54$  mg/dL (3.0 mmol/L) but no information relative to symptoms of hypoglycemia was recorded

- **Severe hypoglycemia (Level 3):** an event requiring assistance of another person to actively administer carbohydrate, glucagon, or other resuscitative actions. During these episodes, the subject has an altered mental status and cannot assist in their care, is semiconscious or unconscious, or experienced coma with or without seizures and may require parenteral therapy. Plasma glucose measurements may not be available during such an event, but neurological recovery attributable to the restoration of blood glucose concentration to normal is considered sufficient evidence that the event was induced by a low PG concentration (PG  $\leq$ 70 mg/dL [3.9 mmol/L])
  - **Severe hypoglycemia requiring medical attention:** a severe hypoglycemic event when subjects require therapy by healthcare professionals (eg, emergency medical technicians, emergency room personnel, etc.)

#### Other Hypoglycemia:

- **Nocturnal hypoglycemia:** any hypoglycemic event (documented symptomatic, asymptomatic, probable symptomatic, or severe hypoglycemia) that occurs between bedtime and waking
- **Relative hypoglycemia:** an event during which typical symptoms of hypoglycemia, that do not require the assistance of another person, are accompanied by PG  $>$ 70 mg/dL (3.9 mmol/L), but these levels may be quickly approaching the 70 mg/dL (3.9 mmol/L) threshold
- **Overall (or total) hypoglycemia:** This optional category combines all cases of hypoglycemia. If an event of hypoglycemia falls into multiple subcategories, the event is only counted once in this category
- **Probable symptomatic hypoglycemia:** An event during which symptoms of hypoglycemia are not accompanied by a PG measurement but that was presumably caused by a blood glucose concentration  $\leq$ 70 mg/dL (3.9 mmol/L).

The determination of a hypoglycemic event as an episode of severe hypoglycemia as defined above will be made by the investigator based on the medical need of the subject to have required assistance and is not predicated on the report of a subject simply having received assistance.

Hypoglycemic events will be recorded in the hypoglycemia module of the eCRF to allow for the collection of comprehensive safety information relating to these events. All episodes of severe hypoglycemia will additionally be reported as SAEs (see Section 9.2.1 for details).

#### **9.4.3. Vital Signs**

For each subject, vital signs measurements (BP, pulse rate, and body temperature) should be conducted according to the Schedule of Activities (Section 2).

Blood pressure and pulse rate should be measured after at least 5 minutes in the supine position.

During any AE of dizziness or posture-induced symptoms, unscheduled orthostatic vital signs should be assessed if possible. If the subject feels unable to stand, supine vital signs only will be recorded. Additional vital signs may be measured during the study if warranted.

#### **9.4.4. *Electrocardiograms***

For each subject, a single 12-lead digital ECG will be collected according to the Schedule of Activities (Section 2). Electrocardiograms must be recorded before collecting any blood samples. Subjects must be supine for approximately 5 to 10 minutes before ECG collection and remain supine but awake during ECG collection. Electrocardiograms may be obtained at additional times, when deemed clinically necessary. All ECGs recorded should be stored at the investigational site.

Electrocardiograms will be interpreted by a qualified physician (the investigator or qualified designee) at the site as soon after the time of ECG collection as possible, and ideally while the subject is still present, to determine whether the subject meets entry criteria at the relevant visit(s) and for immediate subject management, should any clinically relevant findings be identified.

If a clinically significant finding is identified (including, but not limited to, changes in QT/QTc interval from baseline) after enrollment, the investigator will determine if the subject can continue in the study. The investigator, or qualified designee, is responsible for determining if any change in subject management is needed, and must document his/her review of the ECG printed at the time of collection. Any new clinically relevant finding should be reported as an AE.

Any clinically significant findings from ECGs that result in a diagnosis and that occur after dosing of the investigational product should be reported to Lilly, or its designee, as an AE via eCRF.

